### 3.4.2 Handling Missing or Below the Lower Limit of Quantification Data

Blood and urine PK data will follow the same rules for handling of missing or below limit of quantification (BLQ) data.

For PK concentration data, if the actual sampling time is missing, but a valid concentration value has been measured, the concentration value will be flagged and the scheduled time point may be used for the calculation of PK parameters.

In cases of missing pre-dose for the first dose of each treatment period, the missing components may be assumed as zero. For the other cases, the missing data will not be imputed.

For semi-log plots, zero and BLQ values will be imputed as "0.1" for graphical purposes.

For the individual concentration and PK parameter calculation of each treatment period, the following rules will be applied:

- If one or more BLQ values occur before the first measurable concentration, they will be assigned a value of zero.
- If BLQ values occur between measurable concentrations in a profile, the BLQ should be omitted (set to missing).
- If BLQ values occur after the last measurable concentration in a profile, the BLQ should be omitted (set to missing).

For the concentration summary and mean concentration plot preparation of each treatment period, the following rules will be applied:

- Mean concentration at any individual time point or defined time interval will only be calculated if at least half of the patients have valid values (i.e., quantifiable and not missing) at this time point or defined time interval for each treatment period
- In cases where a mean value is not calculated due to the above criterion not being met, the value will be set to missing
- BLQ values will be set to zero.

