## 3.4 Pharmacokinetic Assessment

Of note, systemic absorption of LBP-EC01 may not occur due to the local route of administration and consequently, may result in little to no quantifiable LBP-EC01 concentrations in the blood for a subject's PK profile.

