### 3.4.1 Sample Collections for Pharmacokinetic Analysis

Blood and urine samples for PK will be collected at the times specified in Schedule of Blood and Urine Sampling of the Protocol (Table 2).

Pre-dosing PK samples for urine and blood will be collected after catheterization (if there is no existing catheter), up to 30 minutes prior to dosing. Post-dosing PK samples will be taken within 60 minutes after the catheter is released and re-clamped for 20 minutes to take additional urine and blood samples. 6 hour timepoint ( $\pm 1$  hour) will be collected after 6 hours following the AM dose

Of note, urine PK data will not include volumes since a 20 mL aliquot is taken rather than the whole void urine volume. Patients are allowed to urinate freely outside of the specified collections.

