**Blood and Urine PK Parameters:**

Parameters	Description
$C_{\max, \text{Dose 1}}$	Maximum concentration; determined directly from the concentration time profile; if the maximum concentration occurs at more than one time point, $C_{\max}$ is defined as the first maximum value
$T_{\max, \text{Dose 1}}$	Time to $C_{\max}$ of the first dose; determined directly from the concentration-time profile
$AUC_{0-t}$	Area under the concentration vs time curve (AUC) from predose (time 0) to the last quantifiable concentration ( $C_{\text{last}}$ ) for Dose 1
$C_{\text{trough,max}}$	Minimum measured concentration from Day 1 (only including predose #2) through Day 7
$C_{\max, \text{all}}$	Max post-dose concentration determined from Day 1 through Day 7
$AI_{\text{trough}}$	Accumulation index using $C_{\text{trough}}$ (predose Day 7 / $C_{\text{trough,max}}$ )

The actual collection times will be used for the calculation of PK parameters. The Linear-Log Trapezoidal method (equivalent to the Linear Up/Log Down option in WinNonlin) will be used in the computation of all AUC values.

Additional PK parameters may be determined as appropriate.

The blood and urine PK parameters will be listed and summarized by treatment using descriptive statistics for the PK Population.

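### When no Dose 1 blood sample is quantifiable, the BLQ and tied-maximum rules can place Tmax at the pre-dose sample, and that value enters the summary of a primary PK parameter

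*SAP*

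**What the plan says.** - **BLQ handling (SAP 3.4.2).** The rules for parameters open with "For the individual concentration and PK parameter calculation of each treatment period, the following rules will be applied". The first rule is "If one or more BLQ values occur before the first measurable concentration, they will be assigned a value of zero". BLQ values between or after measurable ones are set to missing.
- **Parameter definitions (SAP 3.4.4, parameter table).** Cmax,Dose 1 is "determined directly from the concentration time profile"; "if the maximum concentration occurs at more than one time point", it "is defined as the first maximum value". Tmax,Dose 1 is the time of that maximum, again read from the profile. The AUC0-t row starts the Dose 1 profile at the pre-dose sample, labelled time 0. The text below the table requires actual collection times.
- **Sampling (SAP 3.4.1).** The pre-dose sample is taken "up to 30 minutes prior to dosing".
- **Expected data (SAP 3.4).** Because administration is local, the plan warns that a profile "may result in little to no quantifiable LBP-EC01 concentrations in the blood".
- **Who is summarised (SAP 3.2.4 and 3.4.4).** The PK Population needs one measurable post-dose concentration and does not say in which matrix. Blood and urine parameters are both summarised on that population.
- **How it is summarised (SAP 3.1.4).** n, mean, median, SD, minimum and maximum are reported. Zeros are dropped only from the geometric mean and its CV%.
- **Status (SAP 2.3.1).** Blood Tmax is listed under the primary endpoints with Cmax and AUC0-t.

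**The concern.** Each rule is ordinary by itself. Together they handle badly a profile with no measured peak. If every Dose 1 value is zero, every sample ties for the maximum, and the earliest of them is the pre-dose sample, taken before any drug was given. The resulting Tmax looks like a very fast time to peak when the correct statement is that no peak was observed.

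Section 3.4 itself expects little or no quantifiable phage in blood, so this may not be a rare case. The study tests no hypothesis (SAP 3.1.5), so the descriptive summaries are its primary PK result. A Tmax summary that mixes real peak times with placeholders from patients who had no peak cannot be interpreted as a time to peak.

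**Working it through.** The SAP gives no Tmax value, so there is no figure of its own to reproduce. The check applies the rules to test profiles and then follows the result into the summary.

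**Step 1: profiles.** Assumed blood samples for Dose 1 are pre-dose, 1.5, 6 and 11.5 h, followed by two samples on later days.

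- *A. Dose 1 all BLQ, later values 50 and 80 PFU/mL.* Reading the first BLQ rule over the treatment period gives 0, 0, 0, 0, 50, 80. Cmax,Dose 1 = max(0, 0, 0, 0) = 0. All four Dose 1 samples tie, the first is pre-dose, and so Tmax,Dose 1 is the pre-dose time.
- *B. BLQ at every sample.* All three BLQ rules refer to a measurable concentration, and there is none. The SAP gives no value. If the analyst extends the zero rule to the whole profile, the result is as in A.
- *C. Measurable after Dose 1 (100 at 1.5 h, 20 at 6 h).* Cmax is 100 and Tmax is 1.5 h. The rules work as intended.

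**Step 2: does anything remove the value?**

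- PK Population: patient A qualifies through the later blood value. Patient B qualifies through a single measurable urine value, because the matrix is not named.
- Zero exclusion (3.1.4): it covers the geometric mean and its CV% only.
- The condition in 3.4.2 that half the patients have valid values governs mean concentrations, not parameters.

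A Tmax of 0 h therefore stays in n, mean, median and minimum.

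**Step 3: size.** Active patients: 36 × 2/3 = 24 (SAP 2.2.4). Assumptions not in the SAP: all 24 are in the PK Population, the true Tmax T is the same in every quantifiable patient, k patients receive a pre-dose Tmax, and pre-dose is coded 0 h.

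Mean = [k × 0 + (24 − k) × T] / 24. The median is the average of the 12th and 13th ordered values.

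| k | Mean, T = 1.5 h | Median, T = 1.5 h | Mean, T = 6 h | Median, T = 6 h |
|---|---|---|---|---|
| 0 | 1.50 | 1.50 | 6.00 | 6.00 |
| 4 | 20 × 1.5 / 24 = 1.25 | 1.50 | 5.00 | 6.00 |
| 6 | 18 × 1.5 / 24 = 1.125 | 1.50 | 4.50 | 6.00 |
| 8 | 16 × 1.5 / 24 = 1.00 | 1.50 | 4.00 | 6.00 |
| 12 | 12 × 1.5 / 24 = 0.75 | (0 + 1.5) / 2 = 0.75 | 3.00 | 3.00 |
| 13 | 11 × 1.5 / 24 = 0.69 | 0 | 2.75 | 0 |
| 18 | 6 × 1.5 / 24 = 0.375 | 0 | 1.50 | 0 |

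The mean shrinks by the factor (24 − k)/24 whatever T is. The minimum is 0 h from the first such patient. The median in this example holds until k = 12 and is 0 h from k = 13.

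**Step 4: after the correction.** If the k values are not determined, mean and median stay at T, and n falls to 24 − k.

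**The case against.** The strongest reply is that the SAP does not force this outcome.

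- **Blood BLQ throughout.** No BLQ rule covers this case, which is the one section 3.4 most clearly foresees. A reader might infer that the plan assigns a pre-dose Tmax to every patient without quantifiable phage in blood. The text does not support that; here it is silent. This part of the reply stands.
- **Profile A.** The companion BLQ rules speak of a profile, and Tmax,Dose 1 is read from the first-dose profile. On that narrower reading a wholly BLQ Dose 1 profile has no first measurable value and the zero rule is not triggered. This reading is possible, but the opening words of the rule set refer to the treatment period, which favours looking across Days 1-7.
- **Discretion.** Section 3.4.4 has parameters determined as appropriate, and section 8 leaves detailed programming specifications to a separate document. Both allow an analyst to leave Tmax blank. Neither states a rule for doing so, and section 8 has the SAS results confirmed in WinNonlin, which calls for one written rule.
- **Negative times.** A reader might infer that the table would show a Tmax of −0.5 h. That needs actual times to override the time 0 label in the AUC row, and every affected sample to lie at the edge of the 30-minute window. A slightly negative value is possible under the actual-time sentence, but −0.5 h is not established, so the illustration uses 0 h.
- **Consequence.** Nothing is tested, individual data are listed, and if half or more of the patients were affected the Cmax,Dose 1 median would also fall sharply. An attentive reader would notice. This limits the harm but does not make the Tmax summary correct.

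**Conclusion.** The point holds in a limited form. For a patient with no quantifiable Dose 1 blood sample but a measurable one later in Days 1-7, the rules read over the treatment period give Cmax,Dose 1 = 0 and Tmax,Dose 1 at the pre-dose time: 0 h, or slightly negative with actual times. For a patient who is BLQ in blood throughout, the SAP has no rule, and the obvious extension gives the same artefact. In either case, once a Tmax is produced, it enters the summary of a primary PK parameter.

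The size depends on how many patients are affected, which the SAP cannot tell us. Any such patient pulls down the mean and sets the minimum. The median is displaced in the illustration only when about half or more of the 24 are affected. The hour values rest on the assumed true Tmax; the proportional loss in the mean does not. No hypothesis test is affected. The correction is still worth making before database lock, because the plan itself anticipates the data that trigger it.

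**What to change.** In sections 3.4.2 and 3.4.4:

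- State that Tmax,Dose 1 is not determined, and is left out of Tmax summaries, when no post-dose Dose 1 concentration in that matrix is quantifiable. This covers both the later-measurable and the wholly BLQ profile.
- Keep Cmax,Dose 1 as 0 for these patients in arithmetic and order statistics.
- State how AUC0-t is treated: 0 by convention, or not determined. Its definition ends at a last quantifiable concentration, which such a profile does not have, so a zero cannot simply be assumed.
- Beside Tmax, report by matrix the number and percentage of patients with any quantifiable Dose 1 sample.

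The cost is a few sentences in the SAP, one programming condition and one extra table row. The Tmax n becomes smaller and may be very small for blood, but the added count shows why.

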#### 3.4.3 *Pharmacokinetic Concentration*

LBP-EC01 concentrations will be determined in both blood and urine by using a plaque forming assay and expressed in units of plaque forming units (PFU)/mL.

Actual sampling times that are outside the sampling time windows may be excluded from concentration summary and mean concentration plotting but will still be used in the calculations of PK parameters and individual concentration plotting.

##### Blood

Individual blood concentrations of LBP-EC01 will be summarized by treatment at each nominal time point for the PK Population descriptively. Individual blood concentrations will also be listed for the PK Population.

Individual blood concentration will be plotted by treatment against actual sampling time points relative to dosing time. Mean ( $\pm$ SD) concentration will be plotted on a linear and semi logarithmic scale against nominal time points by treatment, when available.

##### Urine

Individual urine concentrations of LBP-EC01 will be summarized by treatment at each nominal time point for the PK Population descriptively. Individual urine concentrations will also be listed for the PK Population.

Individual urine concentration will be plotted by treatment against actual sampling time points relative to dosing time. Mean ( $\pm$ SD) concentration will be plotted against nominal time points by treatment, when available.

#### 3.4.4 *Pharmacokinetic Parameters*

The following blood and urine PK parameters of LBP-EC01 will be determined using non-compartmental methods as appropriate:

**Blood and Urine PK Parameters:**

Parameters	Description
$C_{\max, \text{Dose 1}}$	Maximum concentration; determined directly from the concentration time profile; if the maximum concentration occurs at more than one time point, $C_{\max}$ is defined as the first maximum value
$T_{\max, \text{Dose 1}}$	Time to $C_{\max}$ of the first dose; determined directly from the concentration-time profile
$AUC_{0-t}$	Area under the concentration vs time curve (AUC) from predose (time 0) to the last quantifiable concentration ( $C_{\text{last}}$ ) for Dose 1
$C_{\text{trough,max}}$	Minimum measured concentration from Day 1 (only including predose #2) through Day 7
$C_{\max, \text{all}}$	Max post-dose concentration determined from Day 1 through Day 7
$AI_{\text{trough}}$	Accumulation index using $C_{\text{trough}}$ (predose Day 7 / $C_{\text{trough,max}}$ )

The actual collection times will be used for the calculation of PK parameters. The Linear-Log Trapezoidal method (equivalent to the Linear Up/Log Down option in WinNonlin) will be used in the computation of all AUC values.

Additional PK parameters may be determined as appropriate.

The blood and urine PK parameters will be listed and summarized by treatment using descriptive statistics for the PK Population.

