### 2.3 Study Endpoints

#### 2.3.1 *Primary Endpoints*

The primary endpoints involve summarizing the safety and tolerability of AEs and lab parameters, as well as the PK parameters of LBP-EC01. The PK parameters will be assessed as a combined set of all crPhages included in LBP-EC01 in both urine and blood.

The blood PK parameters will include the following assessments of LBP-EC01:

- Maximum concentration ( $C_{max}$ )
- Time to  $C_{max}$  ( $T_{max}$ )
- Area under the concentration versus time curve (AUC) from time 0 to the last measurable concentration ( $AUC_{0-t}$ )

Other PK variables may be calculated as appropriate for the observed data.

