### *3.1.5 Hypothesis Testing*

This is a Phase 1b study and primary outcomes are evaluation of safety, tolerability and PK. No formal hypothesis will be tested.

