## 8 PROGRAMMING SPECIFICATIONS

The creation of analysis datasets and all analyses will be performed using SAS® (version 9.4 or higher). PK parameters will be calculated via SAS® and confirmed with the results of Phoenix WinNonlin™ (version 8.1 or higher).

All available data will be presented in patient data listings which will be sorted by patient and visit date as applicable. Detailed Programming Specifications will be provided in a separate document.

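### C_trough,max is described as a minimum, and AI_trough divides the Day 7 trough by an extreme of a window that contains it, so the index is bounded at 1 on one side

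*SAP*

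**What the plan says.** The parameter table in SAP section 3.4.4 applies to both blood and urine. Its C_trough,max row reads "Minimum measured concentration from Day 1 (only including predose #2) through Day 7". The AI_trough row begins "Accumulation index using" and gives the formula as the Day 7 predose value divided by C_trough,max. The C_max,all row in the same table uses the abbreviation for a maximum in its ordinary sense. No other section redefines either trough parameter.

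Other relevant text:

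- Section 2.2.3: each patient receives 13 doses, the last on the morning of Day 7.
- Section 3.4.1: "Blood and urine samples for PK will be collected at the times specified in Schedule of Blood and Urine Sampling of the Protocol". That schedule is not in the SAP, so the number of troughs is not known here.
- Section 3.4.2: "If one or more BLQ values occur before the first measurable concentration, they will be assigned a value of zero". BLQ values between or after measurable ones become missing.
- Section 3.4.3: "Individual blood concentrations of LBP-EC01 will be summarized by treatment at each nominal time point for the PK Population descriptively", with a parallel statement for urine.
- Section 2.3.1 names Cmax, Tmax and AUC0-t for blood and adds "Other PK variables may be calculated as appropriate for the observed data". AI_trough is not named there.
- Section 3.1.5: "No formal hypothesis will be tested".
- Section 8: PK parameters computed in SAS are to be "confirmed with the results of Phoenix WinNonlin".

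**The concern.** There are two separate faults. First, the name says maximum and the text says minimum, so two programmers could derive opposite quantities and each could point to the SAP. Second, correcting the label or the word does not repair the index. An accumulation ratio is normally read against 1, with values above 1 meaning build-up and values below 1 meaning decline. If the denominator is the lowest or highest value of a set that includes the numerator, one of those directions cannot occur.

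PK is part of the primary objective of this first-in-human study, and AI_trough is the only accumulation index listed. As described, ordinary sample-to-sample variability would appear as accumulation, and a true decline could not appear at all. As labelled, true accumulation could not appear.

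**Working it through.** **The bound.** Let W be the concentrations from predose #2 through Day 7, and c7 the Day 7 predose value. The last dose is on the morning of Day 7, so its predose sample falls on Day 7, and nothing excludes it from W. Therefore min(W) ≤ c7 ≤ max(W), and wherever the ratio is defined:

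- as described: c7 / min(W) ≥ 1;
- as labelled: c7 / max(W) ≤ 1.

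This holds whether W contains only troughs or all samples in the window, because c7 belongs to both sets.

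**Worked series** (illustrative values).

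- Falling 160, 80, 40, 20: as described 20/20 = 1.0; Day 7 over predose #2 is 20/160 = 0.125.
- Rising 20, 40, 80, 160: as labelled 160/160 = 1.0; Day 7 over predose #2 is 160/20 = 8.

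**Size.** The SAP gives no figure to reproduce, so the inputs are assumptions: 5 log-normal troughs, CV 100%, first-order serial correlation 0 / 0.8, a linear trend on the log scale, no BLQ values, and 200,000 simulated patients per setting. With no true accumulation:

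| Denominator | Geometric mean index | Share above 2 | Share below 0.5 | Geometric SD |
|---|---|---|---|---|
| Minimum, Day 7 included | 2.63 / 1.73 | 56% / 34% | 0% / 0% | 2.34 / 1.74 |
| Predose #2 | 1.00 / 1.00 | 28% / 22% | 28% / 22% | 3.25 / 2.47 |

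The maximum version gives a geometric mean of 0.38 / 0.58. The minimum with Day 7 left out gives 2.36 / 1.58.

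Check at correlation 0: the log-scale SD is sqrt(ln(1 + 1²)) = sqrt(ln 2) = 0.8326. The expected maximum of 5 standard normals is 1.163. So the geometric mean is exp(0.8326 × 1.163) = 2.63 for the minimum version and 1/2.63 = 0.38 for the maximum version.

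With a true trend in the same setting:

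- troughs that halve give 1.96 / 1.32 with the minimum, where 0.50 is the truth;
- troughs that double give 0.51 / 0.76 with the maximum, where 2.0 is the truth.

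**Range.** Over 2 to 12 troughs, CV 50% to 200% and correlation 0 or 0.8, with no accumulation, the geometric mean runs from 1.13 (2 troughs, CV 50%, correlation 0.8) to 7.9 (12 troughs, CV 200%, correlation 0) with the minimum. At the same two ends the maximum version gives 0.89 and 0.13. Twelve is the most possible: one trough before each of doses 2 to 13.

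**Second calculation.** With independent errors, 4, 7 or 12 troughs and a log-scale SD of 0.5 or 1.0, the minimum version gives 1.67 to 5.10 under no accumulation and 1.29 to 3.76 under a true halving. The maximum version gives 0.27 to 0.77 under a true doubling. Day 7 over the first trough recovers about 1.0, 0.50 and 2.0 respectively. No simulated profile in either calculation crossed the bound.

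**The case against.** The strongest reply concerns weight. The index is descriptive, is not among the named blood PK endpoints and feeds no test. Concentrations are listed by patient and summarized by nominal time point, so a reader can see a rise or fall directly, subject to the section 3.4.2 rule on when means are calculated. Section 3.4 warns that blood may hold little or nothing quantifiable, so the practical issue may be mainly urine. All of this stands and limits the consequence.

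The simulated sizes rest on assumed inputs, contain no BLQ values and span a wide range. That also stands: they illustrate the direction and possible scale of the bias and do not estimate it for this trial. The bound needs none of them.

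Section 8 defers detail to separate programming specifications, and section 3.4.4 allows additional parameters, so a better ratio could be added. Neither corrects the definition that the SAP states. The WinNonlin confirmation might expose two opposite derivations, but not the bound, which both programs would reproduce.

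The SAP states no neutral value, and Day 7 over the maximum does show whether Day 7 was the highest trough. That is a different quantity from accumulation.

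Finally, predose #2 is one choice of reference. It is noisier per patient, and leaving out patients whose predose #2 is BLQ may drop those with the largest rise. Both are real costs of the remedy.

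**Conclusion.** The concern holds. The label and description of C_trough,max contradict each other, and AI_trough is bounded at 1 on one side under either reading. The bound rests only on the Day 7 predose sample lying in the stated window; it would fail only if that sample were excluded, which the SAP does not say. As described, the index still rises with true accumulation, but it cannot show a decline and variability alone lifts it above 1, so it cannot be read against 1.

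Part of the 56% / 34% of patients above 2 is ordinary variability, since the predose #2 ratio also puts 28% / 22% there. The difference is that the predose #2 ratio spreads equally to both sides. The error should be corrected before the analysis is run, but it does not threaten the safety results or the named blood PK endpoints.

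**What to change.** 1. Reconcile the label and description of C_trough,max.
2. Define AI_trough as the Day 7 predose value divided by predose #2. The table already names that sample, and it lies outside Day 7. Leaving Day 7 out of the minimum alone would lift the bound but not the bias (2.36 / 1.58 above).
3. If minimum and maximum troughs are wanted, report them as separate, correctly labelled rows that are not used in the index.
4. State that the index is not computed when predose #2 or the Day 7 trough is BLQ, and report how many patients this affects. Under section 3.4.2 an early BLQ trough can become zero, which leaves a ratio undefined. This step discloses the problem but does not remove it.

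The cost is SAP wording and one derivation, with no new data. The price is a noisier index per patient (geometric SD 3.25 against 2.34 at correlation 0, and 2.47 against 1.74 at 0.8) and no value for patients whose reference sample is BLQ. Section 1 has the SAP finalized before database lock; a change made after lock would have to be documented in the study report.
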